
Statistical Methods:
	
Sample Size: Up to 50 subjects will be enrolled and treated based on the design of a similar study with a different drug.
 
Populations for Analysis: The Enrolled Population is defined as all subjects who meet inclusion/exclusion criteria during Screening Period and complete Visit 3. All general summaries, except safety and efficacy analyses are based on the Enrolled Population, unless specified otherwise. The Safety Population is a subset of the Enrolled Population defined as those subjects who received at least 1 dose of lixivaptan. This population will be utilized for all safety analyses. The Efficacy Population is a subset of the Safety Population defined as those subjects who have at least 1 eGFR determination during the Baseline Period and have at least 1 eGFR determination during the Follow-up Period. This population will be used for all efficacy analyses. The Pharmacokinetic (PK) Population is a subset of the Safety Population defined as those subjects who had at least 1 on-therapy evaluable PK measurement. The Pharmacodynamic (PD) Population is a subset of the Enrolled Population defined as those subjects who have at least 1 set of urine specific gravity and urine osmolality measurements from the same specimen.
 
Analysis of Primary and Secondary Safety Endpoint: Descriptive statistics (n and percentage) and 95% confidence intervals will be used to present the proportion of subjects who develop ALT levels >3 x ULN that were assessed by the independent HERC to be at least highly likely related to lixivaptan and resulted in discontinuation of the study drug during the Titration or Maintenance Periods. Similarly, descriptive statistics and 95% confidence intervals will be utilized to present the 2 secondary endpoints: the proportion of subjects who develop ALT levels >5 x ULN during the Titration or Maintenance Periods that were assessed by the independent HERC to be related to lixivaptan and resulted in discontinuation of the study drug and the proportion of subjects who develop ALT levels >3 x

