8.2 Populations for Analysis

The following populations will be used for analyzing the data:

The Enrolled Population is defined as all subjects who meet inclusion/exclusion criteria during the Screening Period and complete Visit 3. All general summaries, except safety and efficacy analyses are based on the Enrolled Population, unless specified otherwise.

The Safety Population is a subset of the Enrolled Population defined as those subjects who received at least 1 dose of lixivaptan. This population will be utilized for all safety analyses.

The Efficacy Population is a subset of the Safety Population defined as those subjects who have at least 1 eGFR determination during the Baseline Period and have at least 1 eGFR determination during the Follow-up Period. This population will be used for all efficacy analyses.

The Pharmacokinetic (PK) Population is a subset of the Safety Population defined as those subjects who had at least 1 on-therapy evaluable PK measurement.

The Pharmacodynamic (PD) Population is a subset of the Enrolled Population defined as those subjects who have at least 1 set of urine specific gravity and urine osmolality measurements from the same specimen.

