6 ANALYSIS POPULATIONS

6.1 **Enrolled Population**

The Enrolled Population is defined as all who meet inclusion/exclusion criteria during screening period and complete Visit 3. All general summaries, except safety and efficacy analyses are based on the Enrolled population, unless specified otherwise.

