6.2 Safety Population

The Safety Population is a subset of the Enrolled Population defined as those enrolled subjects who received at least 1 dose of lixivaptan. This population will be utilized for all safety analyses.

6.3 **Efficacy Population**

The Efficacy Population is a subset of the Safety Population defined as those subjects who have at least 1 eGFR determination during the Baseline Period and have at least 1 eGFR determination during the Follow-up Period. This population will be used for efficacy analyses.

6.4 **Pharmacokinetic (PK) Population**

The Pharmacokinetic (PK) Population is a subset of the Safety Population defined as those subjects who had at least 1 on-therapy evaluable PK measurement.

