6.5 Pharmacodynamic (PD) Population

The Pharmacodynamic (PD) Population is a subset of the Enrolled Population defined as those subjects who have at least 1 set of urine specific gravity and urine osmolality measurements from the same specimen.

6.6 **Protocol deviations/violations and exclusions from analysis sets**

A protocol deviation is defined as an unintended or unanticipated departure from the procedures or processes approved by the Sponsor and the Institutional Review Board (IRB) and agreed to by the Investigator. A major deviation occurs when there is not adherence to the protocol by the subject or Investigator that results in a significant, additional risk to the subject.

Major deviations can include the following but not limited to:

- Not adhering to inclusion or exclusion criteria
- Enrollment of the subject without prior Sponsor approval
- Not adhering to Food and Drug Administration (FDA) regulations or ICH Good Clinical Practice (GCP) guidelines
- Subjects not \geq 80% compliant with the prescribed study drug doses during the study

Protocol deviations will be identified and reviewed by the project team prior to database lock.

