8 STATISTICAL METHODS

8.1 General Statistical Conventions

All statistical procedures will be completed using SAS Grid version 9.4 or higher.

Unscheduled visit results will be included in date/time chronological order, within subject listings only. Unscheduled visit shall not be summarized in tables.

Categorical variables will be summarized using number (n) and percentage in each category including missing category if any. All percentages will be rounded to one digit after decimal point. The number and percentage will be presented in the form XX (XX.X %), where the percentage is in the parentheses. If the percentage of a category is "100", then display it as "100" (do not add decimal after 100). 95% confidence intervals will be presented along with frequency counts and percentages for primary and secondary safety endpoints.

Continuous variables will be summarized using number of subjects (n), number of missing subjects, mean, median, standard deviation (SD), minimum, and maximum for continuous variables. All mean and median values will be formatted to one more decimal place than the measured value. Standard deviation values will be formatted to two more decimal places than the measured value. The minimum and maximum will be displayed to the same number of decimal places as the original data. For pharmacokinetic data, geometric mean (with one decimal than the measured value) and geometric CV % (with 1 decimal place) will be presented

additionally.

All general summaries will be presented by Overall, having all the subjects, unless otherwise specified. For safety assessments, the summaries will be presented by titration and maintenance combined, follow-up and overall, unless otherwise specified.

All subject data will be presented in individual subject data listings. All listings will be sorted for presentation in order of dose level if applicable, subject number (including site ID), date/time and visit. The dose level as well as subject's sex, age and race will be stated on each listing. In general, no imputed dates or values will be presented in listings unless specified.

8.2 **Subject Disposition**

The following categories will be summarized only for "Overall" Column. The summary is based on all subjects.

- No. of subjects screened
- No. of subjects who screen failed
- No. of subjects who re-screened
- No. of subjects who complete visit 3 during baseline period (Enrolled Population)
- No. of baseline failure subjects

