- No. of subjects who completed the baseline period

The following categories will be summarized overall. The summary is based on Enrolled population.

- No. of subjects who completed study
- No. of subjects who discontinued from study
- Primary reason for study discontinuation
- No. of subjects who completed treatment
- No. of subjects who discontinued from treatment
- Primary reason for treatment discontinuation
- No. of subjects who entered titration period
- No. of subjects who completed treatment during titration period
- No. of subjects who discontinued treatment during titration period
- No. of subjects who entered maintenance period
- No. of subjects who completed treatment during maintenance period

• No. of subjects who discontinued treatment during maintenance period

In addition, number of subjects in the safety population who completed or discontinued during titration and maintenance period will be summarized by last dose level assigned during the specified period.

A listing of subject disposition will be provided for all subjects, with the extent of their participation in the study and the reason for discontinuation from study or treatment.

Additionally, a listing of inclusion/exclusion criteria will be presented for all subjects.

8.3 **Protocol Deviations**

A summary of subjects excluded from safety population, efficacy population, pharmacokinetic and pharmacodynamic populations will be presented by enrolled population.

A summary of major (key) protocol deviations will be presented for Enrolled population. All protocol deviations will be listed.

8.4 **Demographics and Baseline Characteristics**

Subject characteristics and demographics will be summarized for the Enrolled population. The summary will include descriptive statistics such as the number of subjects (n), mean, SD, median, minimum (min), and maximum (max) for continuous measures and frequency counts and percentages for categorical measures. No formal statistical comparisons will be made among dose levels.

The following demographics will be summarized: Age (years), Height (cm), Weight (kg), Body Mass Index (BMI) (kg/m²), Systolic Blood Pressure (mmHg), Diastolic Blood Pressure (mmHg), Sex, Child bearing potential for female population, Race (Primary, Secondary and subcategory) and Ethnicity.

Baseline disease characteristics include:

- Baseline eGFR
- Baseline AST or ALT levels
- Baseline Total Bilirubin levels
- History of ADPKD

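### As worded, the Safety Population would drop a dosed subject later found to have failed a Screening criterion (minor; wrong as written)

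*SAP*

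**What the plan says.** SAP 6.2 defines the safety set in two layers: "The Safety Population is a subset of the Enrolled Population defined as those enrolled subjects who received at least 1 dose of lixivaptan". It is then used for every safety analysis, which includes the primary hepatic endpoint (SAP 8.6 and 8.6.1). The outer layer is set in SAP 6.1: "The Enrolled Population is defined as all who meet inclusion/exclusion criteria during screening period and complete Visit 3". Protocol 8.2 has the same nesting ("The Safety Population is a subset of the Enrolled Population defined as those subjects who received at least 1 dose of lixivaptan"), and the protocol synopsis has the same eligibility condition ("The Enrolled Population is defined as all subjects who meet inclusion/exclusion criteria during Screening Period and complete Visit 3").

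Other places describe enrolment differently. The disposition list in SAP 8.2 attaches the Enrolled label to Visit 3 alone: "No. of subjects who complete visit 3 during baseline period (Enrolled Population". SAP 8.3 plans this: "A summary of major (key) protocol deviations will be presented for Enrolled population". SAP 6.6 names as one such major deviation: "Not adhering to inclusion or exclusion criteria". Protocol 4.1 gives completion of Visit 3 as the enrolment event in one sentence, and in the next restricts enrolment to subjects who satisfy the criteria.

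**The concern.** A safety set should contain everyone exposed. Here eligibility enters by way of the Enrolled Population, and nothing in either document returns a dosed but ineligible subject to the safety set. In a hepatic safety study with few subjects, losing one can change both numerator and denominator of the primary endpoint. If the failed criterion bears on hepatic risk (for example ALT/AST, bilirubin, hepatitis serology or an interacting drug), the omission could favour the drug.

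The definition is still in force after early termination. SAP 9 cuts the output, but Appendix IV keeps these on the Safety Population: Table 14.3.2.1 (primary and secondary hepatic endpoints), the TEAE tables, the exposure table, and the drug accountability and tolerability/modification listings.

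**Working it through.** **1. Set logic.** Let C = satisfied the entry criteria during Screening, V = completed Visit 3, D = received at least one dose.

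- Enrolled (SAP 6.1, protocol 8.2, synopsis) = C and V.
- Safety (SAP 6.2, protocol 8.2) = Enrolled and D = C and V and D.
- A subject with C = no, V = yes, D = yes is outside Enrolled and therefore outside Safety.

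The condition is tied to Screening. A breach that first appears in the Baseline Period (for example exclusion 17 or 18 at Visit 4) does not make C false, so that subject would stay in both sets if dosed.

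**2. The same subject elsewhere in the plan.**

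| Place | Condition used | Is the subject Enrolled? |
|---|---|---|
| SAP 6.1, protocol 8.2, synopsis | C and V | No |
| SAP 8.2, disposition label | V | Yes |
| SAP 8.2, titration entry and later steps, summarised on Enrolled | presumes those entering titration are Enrolled | Yes, by implication |
| SAP 8.3 with 6.6, eligibility breaches tabulated on Enrolled | possible for a Screening breach only if C is not required | Yes, by implication |
| Protocol 4.1 | V as the event, C as a requirement | Unclear |

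**3. Size.** The plan gives no figure to reproduce. It states neither an ineligibility rate nor the number dosed. SAP 9 gives only 6 subjects entering maintenance, and the planned maximum is 50. I therefore assume 6 to 50 dosed, with one left out. Intervals are exact binomial 95%, as in SAP 8.6.1: lower limit = Beta quantile 0.025 with parameters (x, n − x + 1); upper limit = Beta quantile 0.975 with (x + 1, n − x). For x = 0 the upper limit reduces to 1 − 0.025^(1/n); for example 1 − 0.025^(1/5) = 52.18%.

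| Assumed dosed | Where the event is | All dosed counted | As worded |
|---|---|---|---|
| 6 | omitted subject only | 1/6 = 16.7% (0.42–64.12) | 0/5 = 0% (0–52.18) |
| 6 | one other subject | 1/6 = 16.7% (0.42–64.12) | 1/5 = 20.0% (0.51–71.64) |
| 6 | none | 0/6 = 0% (0–45.93) | 0/5 = 0% (0–52.18) |
| 50 | omitted subject only | 1/50 = 2.0% (0.05–10.65) | 0/49 = 0% (0–7.25) |
| 50 | one other subject | 1/50 = 2.0% (0.05–10.65) | 1/49 = 2.04% (0.05–10.85) |
| 50 | none | 0/50 = 0% (0–7.11) | 0/49 = 0% (0–7.25) |

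The direction is not fixed: the percentage falls if the omitted subject has the event and rises slightly if another subject does. SAP 9 says no statistical analyses will be performed, so the intervals may not be reported. The count and percentage in Table 14.3.2.1 would still change.

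**The case against.** The best defence is that the entry condition records a decision taken at the time: the subject passed the eligibility check at the end of Screening. Protocol 4.2.2 treats failure as a designation given during Screening or Baseline, and a subject who was passed and dosed never received it. On that reading SAP 6.1, 8.2, 8.3 and 6.6 all fit together. No passage directs anyone to remove a dosed subject afterwards; protocol 11.2.2 has such a subject withdrawn from the study and is silent on analysis sets. This is probably what was meant, and it keeps the point minor. But it is not written, and a programmer who follows SAP 6.1 and 6.2 as they stand would reach the opposite result.

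The case is also remote. Eligibility is settled at Visit 2, reviewed with the medical monitor before Visit 3, and confirmed at Visit 5 before drug is dispensed. That stands.

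A reader might infer that the omission would go unseen, because SAP 8.3 plans only this: "A summary of subjects excluded from safety population, efficacy population, pharmacokinetic and pharmacodynamic populations will be presented by enrolled population". A subject outside Enrolled would not appear there, and Appendix IV does not list that summary. The documents do not support that inference. Table 14.1.1.1 is kept on All Subjects and, under SAP 8.2, counts Visit 3 completers. The listings of deviations, adverse events, liver dysfunction, liver chemistry and endpoint criteria are also on All Subjects.

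**Conclusion.** Wrong as written, and minor. Read literally, SAP 6.2 and protocol 8.2 take a dosed subject out of the safety tables if a failed Screening criterion comes to light later. Neighbouring text suggests the opposite intent without stating it. The effect is limited to counts and percentages in Safety Population outputs. Its size is illustrative only, since it rests on an assumed number dosed and on one assumed late finding of ineligibility.

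A reader might go further and infer that a subject has been dropped, or that the hepatic result is biased towards the drug. The documents report no such subject. Bias towards the drug would need a missed breach, dosing, literal exclusion and an event in that same subject.

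**What to change.** In SAP 6.2, remove the nesting in the Enrolled Population and write, for example: *The Safety Population includes every subject who took one or more doses of lixivaptan, regardless of eligibility.* Report eligibility breaches as protocol deviations, as SAP 8.3 already plans. Record the change in SAP 9 and state it in the study report.

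Protocol 8.7 allows the SAP to modify the protocol's plans, and asks for an amendment only for a major change to the primary analysis. This change leaves the endpoint and method as they are and only makes the denominator explicit, so I would not treat it as major. Protocol 8.2 and the synopsis can be aligned if the protocol is amended for another reason; an amendment for this alone would need IRB/EC submission.

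Redefining Enrolled in SAP 6.1 as Visit 3 completion is optional. It would match SAP 8.2 but add a further difference from protocol 8.2, and it is not needed to cure this point.

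Cost: one sentence in SAP 6.2 and a note in SAP 9 and the report. No new data are needed.

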6.5 Pharmacodynamic (PD) Population

The Pharmacodynamic (PD) Population is a subset of the Enrolled Population defined as those subjects who have at least 1 set of urine specific gravity and urine osmolality measurements from the same specimen.

6.6 **Protocol deviations/violations and exclusions from analysis sets**

A protocol deviation is defined as an unintended or unanticipated departure from the procedures or processes approved by the Sponsor and the Institutional Review Board (IRB) and agreed to by the Investigator. A major deviation occurs when there is not adherence to the protocol by the subject or Investigator that results in a significant, additional risk to the subject.

Major deviations can include the following but not limited to:

- Not adhering to inclusion or exclusion criteria
- Enrollment of the subject without prior Sponsor approval
- Not adhering to Food and Drug Administration (FDA) regulations or ICH Good Clinical Practice (GCP) guidelines
- Subjects not \geq 80% compliant with the prescribed study drug doses during the study

Protocol deviations will be identified and reviewed by the project team prior to database lock.

7 STATISTICAL CONSIDERATIONS AND ANALYSIS

7.1 Derived General Variables

The below table (Table 4) provide the list of derived variables for demographic and baseline characteristics, various duration derivations, drug compliance, baseline derivations and other important derivations applicable for this study.

Variables	Formula					
Demographic characteristics						
Age at informed consent (in years)	Age = year of informed consent – year of birth					
BMI (kg/m ²)	weight (kg)/[height (m)] 2					
Derivation of Duration						
Study Duration (Days)	(Date of Last Visit – Date of informed consent) + 1					
Study day at any visit	Date of interest – date of first dose of study drug. One day is added if this difference is ≥ 0					
Adverse event duration (in days)	Event end date - Event onset date + 1.					
Duration of Exposure						
Duration of Exposure (days) in Titration Period	(Date of last administration of study drug – Date of first administration of study drug) +1, during the 6 week titration period					
Duration of Exposure (days) in Maintenance Period	(Date of last administration of study drug – Date of first administration of study drug) +1, during the 52 week maintenance period					
Treatment Compliance						
Treatment Compliance	(Total No. of capsules dispensed – Total No. of capsules returned)*50/total assigned dose*100 where, total assigned dose will be derived by sum of (AM+PM dose)*duration of this dose level for all different dosing levels					
eGFR Baseline and Fin	al Assessment Derivation (Appendix I)					
Baseline eGFR	Mean of 3 eGFR assessments (Visit 3, Visit 4 & Visit 5) obtained during the baseline period					
Final Assessment eGFR	Mean of 3 eGFR assessments (Visit 25, Visit 26 & Visit 27) obtained during the follow-up period					
Baseline Derivations						

Table 4: Derived Variables

Baseline	Latest non-missing measurement prior to first dose of study drug administration	
Change from baseline	Test Value at Post baseline value – Baseline Value	
Geometric Coefficient of Variation (CV%) for Pharmacokinetic data		
Geometric CV%	CV (%) =100× $\sqrt{\exp(\hat{\sigma}^2) - 1}$, where $\hat{\sigma}^2$ denotes the variance of the natural log-transformed values.	
	the natural log-transformed values.	

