4.1.1 Inclusion Criteria

In order to qualify for enrollment in this study, each subject must meet the following inclusion criteria:

1. Male or female, between 18 and 65 years of age (inclusive) at the time of Screening.
2. Female subjects must:
 - a. not be pregnant, lactating, or breastfeeding.
 - b. be either postmenopausal (defined as amenorrhea for ≥ 12 months), surgically sterile (defined as having undergone hysterectomy and/or bilateral oophorectomy), or if of child-bearing potential (WOCBP) must agree to practice appropriate methods of birth control or remain abstinent (only if this is the usual and preferred lifestyle of the participant) during the study and for 30 days after the last dose of study drug. Acceptable forms of contraception include any of the following:
 - hormonal contraceptives (i.e., oral, intravaginal, transdermal, injectable, implantable)
 - double barrier methods of non-hormonal contraception are permitted in this study.
 - male or female condom with spermicide (cream, spray, gel, suppository, contraceptive sponge, or polymer film)
 - diaphragm, cervical cap, or contraceptive sponge with spermicide (with or without a condom)
 - intrauterine device (IUD), including progestin-containing intrauterine devices
 - intrauterine hormone-releasing system (IUS)
 - male sexual partner who has been vasectomized for at least 3 months prior to Screening and who has obtained a follow-up negative sperm

count

- bilateral tubal ligation
 - Essure[®] procedure (tubal occlusion).
3. Male subjects and their female partners of childbearing potential must also use the contraceptive methods listed above or remain abstinent (only if this is the usual and preferred lifestyle of the participant) during the study and for 30 days after the last dose of study drug.
 4. Diagnosis of ADPKD confirmed by previous treatment with tolvaptan specifically for that indication and supported by evidence from any imaging modality or genetic analysis.
 5. Screening eGFR ≥ 20 ml/min/1.73m².
 6. Body mass index (BMI) between 18 and 35 kg/m² (inclusive) at the time of Screening.
 7. Documented history of:

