7.3.2 Demographics and Medical History

Medical history and demographic data, including initials, sex, age, race, and ethnicity will be recorded at the Screening Visit 1 (Table 1).

Medical and medication history will be assessed as related to the eligibility criteria in Section 4.1. Medical history will include documented history of abnormal liver chemistry test results while on tolvaptan, history of permanent discontinuation of tolvaptan due to abnormal liver chemistry test results, history of any re-challenge with tolvaptan or development of DILI on tolvaptan. As data permit, information on the duration of tolvaptan use prior to discontinuation should be included.

Other than tolvaptan, medication history will include all medications taken within 30 days prior to Screening (except for the longer periods specified for Exclusion Criteria 7, 8, and 9; see Section 5.7) and history of drug, alcohol, and tobacco use.

An update to medical history, including medication review, will be performed at Screening Visit 2 to verify subject eligibility.

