11 APPENDICES

11.1 Appendix I: Chronic Kidney Disease Classification Criteria

This study uses the 2009 CKD-EPI creatinine equation (Levey A, which is recommended by the KDIGO Clinical Practice Guidelines for Management of Chronic Kidney Disease.

The CKD-EPI equation is:

$$eGFR = 141 \times min\left(\frac{Scr}{\kappa}, 1\right)^{\alpha} \times max\left(\frac{Scr}{\kappa}, 1\right)^{-1.209} \times 0.993^{Age} \times 1.018 \text{ (if female)} \times 1.159 \text{ (if black),}$$

where Scr is serum creatinine, κ is 0.7 for females and 0.9 for males, α is -0.329 for females and -0.411 for males, min indicates the minimum of Scr/ κ or 1, and max indicates the maximum of Scr or 1.

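### SAP 7.1 derives age by subtracting calendar years, so displayed age is one year too high for any subject whose birthday falls after the consent date

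*SAP*

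**What the plan says.** The derived-variables table in SAP 7.1 labels the variable as age, in years, at informed consent, and defines it as "Age = year of informed consent – year of birth". No birthday adjustment appears there or elsewhere in the SAP.

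The protocol collects age directly. Section 7.3.2 states: "Medical history and demographic data, including initials, sex, age, race, and ethnicity will be recorded at the Screening Visit 1". The age limit is Inclusion Criterion 1 in Protocol 4.1.1: "Male or female, between 18 and 65 years of age (inclusive) at the time of Screening".

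SAP 8.1 carries age widely: "The dose level as well as subject's sex, age and race will be stated on each listing". SAP 8.4 puts age in the demographic summary. SAP section 9 cuts the outputs after early termination, but Appendix IV keeps Table 14.1.2.1.1 and Listing 16.2.4.1, both for demographic characteristics.

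Protocol Appendix 1 and SAP Appendix I print the CKD-EPI equation with Scr divided by kappa inside both the min and the max term. The legend below it defines min with kappa, but then says "max indicates the maximum of Scr or 1". The wording is the same in both documents.

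**The concern.** A difference of calendar years is not an age. It equals attained age only if the birthday has been reached by the consent date. Otherwise it is one year too high. The label promises age at consent, and the formula does not deliver it for those subjects.

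What is at stake is the accuracy of individual ages in the final outputs. After early termination those outputs are mostly subject listings for a very small study, so a single wrong age is easy to see. A displayed 66 next to an upper limit of 65 invites a query that the study did not earn.

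The legend slip is separate and smaller: one sentence disagrees with the formula above it.

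**Working it through.** The plan states no figure for this point, so there is nothing to reproduce. The check applies the formula as written.

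**Age: size of the error**

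Inputs: the SAP 7.1 formula and the 18 to 65 range in Protocol 4.1.1. The distribution of birthdays and consent dates is not in the documents and is assumed.

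Completed age = (year of consent − year of birth) − 1 if the birthday falls after the consent date, and − 0 otherwise. The SAP formula leaves out the last term, so its error is +1 or 0.

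- Upper limit: born 15 Dec 1955, consent 15 Mar 2021. Completed age is 65; the formula gives 2021 − 1955 = 66.
- Lower limit: born 15 Dec 2003, consent 15 Mar 2021. Completed age is 17; the formula gives 2021 − 2003 = 18.

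**Age: share of subjects affected**

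With birthdays spread evenly over 365 days and consent on day d of the year, the share affected is (365 − d)/365.

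| Consent date | d | Share one year too high |
|---|---|---|
| 15 Jan | 15 | 350/365 = 95.9% |
| 15 Mar | 74 | 291/365 = 79.7% |
| 15 Jun | 166 | 199/365 = 54.5% |
| 15 Sep | 258 | 107/365 = 29.3% |
| 15 Dec | 349 | 16/365 = 4.4% |

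Averaged over evenly spread consent dates, the share is 182/365 = 49.9%. The mean overstatement is therefore about 0.5 year.

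**Legend: what it would do if coded literally**

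Inputs: kappa 0.7 (female) and 0.9 (male), and the exponent −1.209, from either appendix. Scr is taken in the unit in which kappa is expressed. For Scr of 1 or more, the ratio of legend to equation is Scr^−1.209 / (Scr/kappa)^−1.209 = kappa^−1.209.

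- Men: 0.9^−1.209 = 1.136, or +13.6%.
- Women: 0.7^−1.209 = 1.539, or +53.9%.
- At age 50, without the race factor, and Scr 2.0: men 42.9 against 37.8; women 43.7 against 28.4.
- At Scr no greater than kappa there is no difference.

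These figures describe a misreading. The equation printed directly above the legend gives the correct values.

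**The case against.** The best defence of the age formula is that it may be all the data allow. The SAP mentions only year of birth, and Protocol 7.3.2 lists age but no birth date. If only the year is held, completed years cannot be derived. That stands, but it does not rescue the formula, because the protocol already has age itself recorded at Visit 1.

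It is also fair to say that nothing inferential depends on age. Safety and efficacy are descriptive (SAP 8.6 and 8.7.1.1), and age enters no model, test or subgroup. That stands in full.

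A reader might infer three stronger things that the documents do not support:

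- **False eligibility breaches.** SAP 6.6 gives "Not adhering to inclusion or exclusion criteria" as an example of a major deviation, so a displayed 66 might seem to create one. But eligibility is settled at the site, with a medical-monitor review of each subject (Protocol 4.1). Deviations are documented by the clinical monitor (Protocol 11.2.2) and reviewed by the project team before lock (SAP 6.6). No section derives either from the SAP age variable.
- **Wrong eGFR for entry or efficacy.** Protocol 7.1.1 has the central laboratory calculate the eGFR reported to investigators by the CKD-EPI formula, and both documents print that formula correctly. No section says the SAP-derived age feeds it. If it did, one extra year would lower eGFR by 0.7% (factor 0.993). SAP section 9 rules out statistical analyses, and Appendix IV lists no change-in-eGFR table.
- **A unit error.** SAP 8.6.6 calls for SI units when laboratory data are summarised. It does not say that creatinine is converted before eGFR is derived.

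**Conclusion.** The age derivation is wrong as written, and the consequence is minor. Followed exactly, it adds one year to the displayed age of every subject whose birthday falls after consent, and it never subtracts one. That much follows from the formula alone.

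The proportion does not. About half rests on evenly spread birthdays and consent dates, which the documents do not give; by consent date the share is roughly 4% to 96%. SAP section 9 reports only 6 participants in the maintenance period, so with so few subjects the actual share could lie well away from half.

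The effect stops at display: the demographic table, the demographic listing and the age shown on each listing. The legend is a clerical inconsistency. Nothing in the documents shows that any eGFR was or would be calculated from it.

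**What to change.** - **SAP 7.1:** replace the age formula with the age recorded at Visit 1. Where the full birth date is held, completed years from date of birth to date of consent would serve equally well. Either removes the error for every subject; the 15 Dec 1955 example then shows 65.
- **Protocol Appendix 1 and SAP Appendix I (editorial):** change the legend so that max is the maximum of Scr/kappa or 1. The printed equation stays as it is.

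The cost is one line of derivation code and short wording edits. Design, conduct and planned analyses do not change.
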